1.0 Study Summary

Study Title	Eating Disorder Individualized Therapeutics-Naltrexone Neuroimaging
Study Design	Open label, prospective trial
Primary Objective	Modulation of reward system measured by fMRI
Research Intervention(s)/ Investigational Agent(s)	Naltrexone 50 mg oral tablet x 1
Study Population	Adolescents aged 13-21 years
Sample Size	Pre-screening up to 1000 individuals, Up to n=50
Study Duration for Individual Participants	1 study visit (~10 hours)
Study Specific Abbreviations/ Definitions	FMRI – functional magnetic brain imaging BOLD – blood oxygenation level dependent AN – anorexia nervosa BN – bulimia nervosa BED – binge eating disorder ED – eating disorder ROI – region of interest MID – monetary incentive delay PFV – passive food view EPSI – eating pathology symptom inventory AKR – aldoketoreductase OPRM – opioid receptor mu NTX - naltrexone

2.0 Objectives

The overall goal of this project is to generate pilot data to support the development of fMRI as a pharmacodynamic biomarker of opioid antagonism in adolescents with ED, which will be accomplished through the following specific aims (SA):

SA1. Define the extent of within individual reward system modulation and identify the brain region most responsive to opioid antagonism in adolescents with binge/purge ED. We will use fMRI to detect percent blood oxygenation level dependent (%BOLD) changes pre- and post-opioid antagonist treatment (i.e., naltrexone) within individuals during a food reward and general reward-related task using regions of interest (ROI) analysis. We hypothesize that the anterior cingulate cortex (ACC) will be most responsive to naltrexone in adolescents with ED during food reward.

SA2. Determine the fMRI reward paradigm most sensitive to opioid antagonism in adolescents with binge/purge ED. Using the method described in SA1, we anticipate that the food paradigm will be more sensitive (e.g., higher t-score) in reward ROI to opioid antagonism in our target population.

SA3. Describe the naltrexone exposure-brain response relationship using fMRI in adolescents with binge/purge ED. We will link pharmacokinetic (PK) parameters of exposure with %BOLD change in subjects during the reward paradigms using ROI analysis. Based on our preliminary data suggesting

SHORT TITLE: Naltrexone Neuroimaging

widely variable maximum plasma concentrations (C_{max}) of naltrexone in adolescents with ED (17-fold), we hypothesize that reduced C_{max} will be associated with reduced activation in reward-related ROIs.

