4.0 Study Endpoints

Outcomes	Exploratory Outcomes

Primary:
 
• RESPONSE (SA1) - defined by $\Delta\%BOLD$ pre/post-ntx in ROI 
Secondary:
 
▪ ROI (SA1) - defined by coordinates with largest response▪ OPTIMAL PARADIGM (SA2) – paradigm (PFV or MID) resulting in larger response▪ EXPOSURE (SA3) – defined by ntx C_{max}	
▪ RESPONSE x OPRM1 genetic variation▪ RESPONSE x metabolomic profile▪ RESPONSE x impulsivity▪ RESPONSE x negative urgency▪ RESPONSE x delayed discounting▪ EXPOSURE x AKR1C4 genetic variation▪ EXPOSURE x metabolomic profile

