21.0 Withdrawal of Subjects

Participants may withdrawal at any time during the study. To withdrawal participants will notify the study team in writing that they wish to withdrawal. Study procedures will cease. Any data collected will be retained for potential analysis.

22.0 Data Analysis:

Outcome analyses. Outcomes are defined per Table 2. SA1. *Response*. fMRI data will be analyzed in AFNI in two ways: 1) region of interest (ROI) analysis in *a priori* reward ROIs including the ventromedial prefrontal cortex, ACC and striatum and 2) exploratory whole brain analysis to identify regions outside the reward network that may also respond to naltrexone (e.g., insula, dorsolateral prefrontal cortex, dorsal ACC). We have chosen to use a pre-defined ROI analysis which will be selected from a meta-analysis of passive viewing food tasks and MID studies using neurosynth.org or similar(29). Although ROI approaches do present challenges in fMRI analyses, this hypothesis-driven approach has been chosen to focus the primary analysis to test targeted reward related changes associated with treatment. Exploratory analysis described below will use advanced fMRI analysis approaches to take advantage of the richness of the whole-brain data. SA2. *Optimal paradigm*. The %BOLD changes will be compared between paradigms by LMM using paradigm (PFV, MID) and time (pre, post) as fixed-effects, and random individual and/or paradigm intercepts. SA3. The changes in %BOLD and changes in *Exposure* (log-scale) will be correlated by Pearson's correlation coefficient; the 95% CI will be estimated by non-parametric bootstrap using the bias-corrected and accelerated method.

PKPD analysis. Kinetica 5.0 or similar software will be used to model PK parameters (e.g., C_{max} , AUC_{0-inf}).

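### SA1 predicts that the ACC responds most, but the plan names the region by its largest observed response and compares no regions, so a winner is always named

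*Combined protocol and SAP*

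**What the plan says.** Section 2.0 sets SA1 the task to "identify the brain region most responsive to opioid antagonism in adolescents with binge/purge ED" and makes a directional prediction: "We hypothesize that the anterior cingulate cortex (ACC) will be most responsive to naltrexone in adolescents with ED during food reward".

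Section 4.0 lists the region as a secondary outcome: "ROI (SA1) - defined by coordinates with largest response". No test, margin or interval goes with it.

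For SA1, Section 22.0 names the software, an analysis of a priori "reward ROIs including the ventromedial prefrontal cortex, ACC and striatum", and an exploratory whole-brain analysis. The ROIs come from an outside source, "which will be selected from a meta-analysis of passive viewing food tasks and MID studies using neurosynth.org or similar", and the final list and boundaries are not given. The whole-brain analysis is meant to "identify regions outside the reward network that may also respond to naltrexone (e.g., insula, dorsolateral prefrontal cortex, dorsal ACC", so part of the ACC is placed outside the network to which the ACC ROI belongs.

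The only comparative model in Section 22.0 belongs to SA2: "LMM using paradigm (PFV, MID) and time (pre, post) as fixed-effects, and random individual and/or paradigm intercepts". It has no region term. SA3 is a correlation of change with exposure.

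**The concern.** Calling the ACC the most responsive region asserts that its change is larger than the change in each other region. The plan never estimates that difference. It ranks the observed responses and takes the top one, and a top one always exists, whether or not the regions differ and whether or not the drug does anything.

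Testing each region separately would not close the gap. A significant change in the ACC beside a non-significant change in the striatum does not show that the ACC changed more, even with locked masks and a multiplicity rule.

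Two things are at stake. The SA1 hypothesis could be reported as supported when the data do not separate the regions. And the response quoted at a location chosen for being largest is overstated when the candidates are close together. The study exists to produce pilot data for a biomarker, so the region and its response are among its main products.

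**Working it through.** The plan gives no power, error rate, effect size or SD for SA1, so there is no figure to reproduce.

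**Inputs.** Three named ROIs (Section 22.0, where the list is open-ended). At most 50 participants (Section 5.0), taken here as n = 50. Assumed, because the documents are silent: changes in SD units with equal SDs, correlation between regional changes of 0.3 to 0.6, and the true changes stated below.

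**1. How often the ACC is named when regions are equal.** For k exchangeable regions, P(ACC first) = 1/k by symmetry.
- k = 3: 0.33; k = 4: 0.25; k = 5: 0.20; k = 6: 0.17.
- Simulation with k = 3 gives 0.332 to 0.335 at correlations from 0 to 0.8, and 0.334 when all three share a true response of 0.4 SD. The result does not need a null drug effect.
- Unequal noise moves it. With equal true changes of zero and an ACC SD of 0.5 to 2 times the others, the ACC is named 30% to 41% of the time on signed change and 11% to 62% on absolute change. Unequal correlations (0.3 and 0.7) give 30% to 39%.

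**2. Bias in the winner's response.** For three equal regions with common true change μ (in SD units) and correlation ρ, the expected largest mean is μ + 0.846 × √((1 − ρ)/n), where 0.846 = 3/(2√π) is the expected maximum of three independent standard normals.
- ρ = 0.3: 0.846 × √(0.7/50) = 0.100.
- ρ = 0.6: 0.846 × √(0.4/50) = 0.076.
- At μ = 0.3 the winner averages 0.376 to 0.400, an overstatement of 25% to 33%.
- At μ = 0.8 the same bias is 0.076/0.8 to 0.100/0.8, about 10% to 13%.
- With the ACC at 0.6 and the others at 0.3, simulation gives 0.602 to 0.605, a bias below 1%.

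**3. Ranking is weak evidence when the lead is small.** With a true ACC lead of 0.1 SD (0.4 against 0.3), the ACC is named 59% to 67% of the time, but beats both rivals in one-sided 5% paired tests only 6% to 8% of the time.

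**4. A rule that requires the ACC to beat every rival.** Take paired contrasts with both two-sided 95% CIs above zero.
- Three equal regions: false confirmation falls from 33% to 0.3%–0.5% (n from 20 to 50, correlation from 0 to 0.8).
- Least favourable case (one rival equal, the other far below): 2.6% simulated, 2.5% nominal.
- True ACC lead of 0.3 SD, n = 50, correlation 0.3 to 0.6: supported about 25% to 48% of the time, against 93% to 98% named by ranking.
- True lead of 0.5 SD, n = 50: supported 55%, 89% and over 99% of the time at correlations 0, 0.5 and 0.8.

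**The case against.** The strongest reply is that this is a pilot and the region is a secondary outcome. Choosing a candidate by rank is a legitimate pilot purpose, and ranking does it well when there is a real lead: 93% to 98% correct for a lead of 0.3 SD. This stands for selection. It does not stand for the stated hypothesis, which needs some rule that separates a real lead from a chance ranking. A ranking labelled descriptive would be acceptable.

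A second reply concerns the remedy. Requiring ACC minus rival to be positive assumes that response means a rise in %BOLD. The plan does not say so: Section 3.0 describes the drug as interrupting the reward circuit, while the SA3 hypothesis, read literally, links lower exposure to lower activation. If naltrexone lowers the signal, a naive positive-difference rule misleads. In one-sided 5% tests, an ACC change of −0.6 SD against −0.3 SD elsewhere is supported 0% of the time, while −0.1 SD against −0.5 SD, where the ACC responds least, is declared most responsive 63% to 88% of the time. This stands in full, so direction must be fixed first. An interval level is needed too: if only the point estimates must exceed zero, the rule is the same as ranking.

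Third, the sizes are conditional. A reader might infer a flat one-in-three false-confirmation rate, or an overstatement of a quarter to a third. The documents support neither as a general figure: the ROI list is open, noise may differ, the outcome refers to coordinates (a voxel search would favour larger or noisier ROIs), and the bias shrinks as the effect or the lead grows. Large null peaks computed over hundreds of independent locations would rest on an independence that nothing in the plan supports.

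**Conclusion.** The point holds. SA1 states a comparative hypothesis, the outcome definition settles it by the largest observed value, and the analysis section contains no comparison of regions. A winner is therefore guaranteed. Equal regions with similar noise name the ACC about 1/k of the time, about one in three for the three listed ROIs. The selected response is overstated by 25% to 33% at n = 50 with a common 0.3 SD change and correlation 0.3 to 0.6, by about 10% to 13% at 0.8 SD, and negligibly when one region clearly leads. All SDs, correlations and effects here are assumptions.

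A reader might also infer that the primary outcome is estimated in a region picked from the same data, or that a later trial will be sized on the peak. The documents do not say either. Section 22.0 describes a pre-defined ROI analysis for the primary question, and no section sets out how a later trial would be sized. The change should be made, but it concerns how one secondary conclusion is reached, not the validity of the study.

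**What to change.** In the SA1 part of Section 22.0, before analysis:

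1. State the ROI list, including the ACC boundary relative to dorsal ACC; the scale (%BOLD or standardised change), since regions can rank differently on the two; and the direction of response (a pre-specified sign, or magnitude of change).
2. For the passive food view data, estimate the within-person contrast of the ACC with each other a priori ROI, oriented so that positive means a larger ACC response in the stated direction, each with a two-sided 95% CI.
3. Claim that the ACC is most responsive only if the lower limit of every contrast is above zero. No alpha adjustment is needed, because all must hold.
4. Otherwise report the ranking as descriptive, with bootstrap probabilities of each region being first.
5. Estimate the response at any data-selected peak by leave-one-participant-out, or label it as selected and biased upward.

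The cost is SAP wording and a short analysis of data that will already be extracted; no new participants or scans are needed. The downside is that the hypothesis will be declared supported less often, as the working shows for a true lead of 0.3 SD. The descriptive ranking remains available for choosing a candidate region.

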3.0 Background

Naltrexone shows promise in treatment of binge eating and purging. Previous studies have demonstrated that naltrexone, a drug that interrupts the opioid reward circuit, reduces binge eating and purging in adults (1-3). Our recent retrospective case series revealed that naltrexone reduced binge/purge behaviors in approximately 60% of adolescents with no serious side effects (4). However, the patient-specific factors associated with response vs. non-response remain to be elucidated.

Naltrexone systemic exposure is highly variable. Preliminary data from our current naltrexone pharmacokinetic study demonstrate significant interindividual variability in the rate and extent to which naltrexone is absorbed in adolescents with ED. With systemic exposure varying by 16-fold, pharmacokinetic differences may contribute to variability in drug response.

Biomarkers of brain response are lacking. Opioid receptor binding studies done in adults using positron emission tomography (PET) show nearly 100% mu opioid receptor (OPRM) blockade with naltrexone 50 mg (5); however, 1 in 3 adolescents with ED fail to respond at this dose (4) and higher doses may be necessary to reach therapeutic effect in certain individuals (6, 7). Thus, biomarkers of brain response are critically needed to understand the impact of the opioid reward system, and opioid antagonism in adolescents with eating disorders.

Next Steps. Pharmacodynamic biomarkers of brain response are lacking yet are critically needed to untangle factors associated with response vs. non-response and advance precision therapeutics. This study will initiate the development of a biomarker (i.e., neuroimaging) of opioid antagonism in adolescents with eating disorders that will aid in drug development and repurposing.

4.0 Study Endpoints

Outcomes	Exploratory Outcomes

Primary:
 
• RESPONSE (SA1) - defined by $\Delta\%BOLD$ pre/post-ntx in ROI 
Secondary:
 
▪ ROI (SA1) - defined by coordinates with largest response▪ OPTIMAL PARADIGM (SA2) – paradigm (PFV or MID) resulting in larger response▪ EXPOSURE (SA3) – defined by ntx C_{max}	
▪ RESPONSE x OPRM1 genetic variation▪ RESPONSE x metabolomic profile▪ RESPONSE x impulsivity▪ RESPONSE x negative urgency▪ RESPONSE x delayed discounting▪ EXPOSURE x AKR1C4 genetic variation▪ EXPOSURE x metabolomic profile

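### SA2 seeks the paradigm most sensitive to naltrexone, but Sections 4.0 and 22.0 judge it by unstandardised change in %BOLD, which can name a task that detects the drug no better, or worse

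*Combined protocol and SAP*

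**What the plan says.** Section 2.0 sets SA2 as: "Determine the fMRI reward paradigm most sensitive to opioid antagonism in adolescents with binge/purge ED". The accompanying hypothesis is that "we anticipate that the food paradigm will be more sensitive (e.g., higher t-score) in reward ROI to opioid antagonism". SA2 also says that it uses the SA1 method, which is change in %BOLD within regions of interest.

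Section 4.0 lists the primary outcome as "RESPONSE (SA1) - defined by $\Delta\%BOLD$ pre/post-ntx in ROI" and the secondary outcome OPTIMAL PARADIGM as the "paradigm (PFV or MID) resulting in larger response". No scaling by variability is stated.

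Section 22.0 gives the SA2 analysis: "The %BOLD changes will be compared between paradigms by LMM using paradigm (PFV, MID) and time (pre, post) as fixed-effects", with "random individual and/or paradigm intercepts". It does not mention a standardised effect, a separate variance for each paradigm, or a rule for turning the model output into a named winner. The a priori regions are "reward ROIs including the ventromedial prefrontal cortex, ACC and striatum"; which of them decides SA2 is not stated.

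Section 9.0 expects PFV to engage food-cue regions such as prefrontal cortex, and MID to engage the striatum in particular. It also says that the data will support the choice of paradigm for later work.

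**The concern.** Sensitivity to a drug is a signal-to-noise property: how far the mean change stands out from its variability between people. Size of response is only the numerator. The two give the same ranking when the tasks have equal variance in change, and can part when they do not.

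Nothing in the documents puts the tasks on a common scale. One is passive viewing. The other is an incentive task with anticipation and receipt phases. If MID simply produces larger %BOLD contrasts, its changes and their SD may both be larger, with no gain in detection. If its change is somewhat larger but its SD much larger, it detects naltrexone less well and can still be named optimal.

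What SA2 delivers is the paradigm for future trials. Choosing the less sensitive task means a larger sample later for the same power.

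**Working it through.** **Inputs.** The documents state no SD, effect size, alpha or power for SA2, so there is no planned figure to reproduce. From the documents: maximum n = 50 (Section 5.0). Assumed throughout: normally distributed changes, between-task correlation 0.2, and a winner named by point estimate.

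**Formulas.** For each task, dz = mean change / SD of change, and paired t = dz × √n. When both changes have the same direction, the probability that MID shows the larger raw mean is approximately Φ[(|MID mean| − |PFV mean|) / SE], with SE = √[(SD₁² + SD₂² − 2 × 0.2 × SD₁ × SD₂) / n].

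**Worked case.** PFV −0.10 (SD 0.20); MID −0.15 (SD 0.40).
- PFV: dz = 0.50, |t| = 0.50 × √50 = 3.54. MID: dz = 0.375, |t| = 0.375 × √50 = 2.65. PFV is the more sensitive task.
- SE = √[(0.04 + 0.16 − 0.032) / 50] = 0.058. The probability that MID has the larger raw mean is Φ(0.05 / 0.058) = 0.81.
- In simulation the raw rule names PFV in about 20% of trials and the t-score rule in about 75%. They disagree in 55% (41% at n = 25).
- For 80% power with a two-sided 5% paired t-test, dz = 0.50 needs about 34 participants and dz = 0.375 about 58. The task usually chosen needs about 58/34 = 1.7 times as many.

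**Other cases by simulation, n = 50.** Entries are mean/SD of change.

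| PFV | MID | Rules disagree |
|---|---|---|
| −0.15/0.20 | −0.05/0.20 | 0.3–0.4% |
| −0.15/0.20 | −0.08/0.25 | 3% |
| −0.10/0.20 | −0.06/0.25 | 9% |
| −0.10/0.20 | −0.10/0.20 | 12% |
| −0.10/0.20 | −0.10/0.30 | 31% |
| −0.10/0.20 | −0.10/0.40 | 41% |
| −0.10/0.20 | −0.15/0.40 | 55% |

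The 12% row is not harm: the tasks are identical and either choice is right.

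**Gain only.** With MID at −0.20 (SD 0.40), both tasks have |t| = 3.54. The raw rule names MID with probability Φ(0.10 / 0.058) = 0.96. The t-score rule splits evenly.

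**Does the mixed model restore a t-score?** A model with a random individual intercept, a paradigm-by-time interaction and one common residual variance was fitted to data built with PFV −0.10 (SD 0.20), MID −0.15 (SD 0.50) and uncorrelated changes. Both task changes received the same SE, 0.054. The z values were −2.79 for MID and −1.86 for PFV. The paired t values in the same data are −2.12 and −3.54, the reverse order. With a common SE, the model ranks by raw size.

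**The case against.** Four objections carry weight.

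- **The t-score is only an example.** It appears inside an anticipated result, not as a decision rule, and SA2 refers back to the %BOLD method of SA1. This stands. A reader might infer two fixed rules in conflict; the documents support only a mismatch between the aim and an incompletely defined endpoint. Still, sensitivity is the aim itself, and its only illustration is standardised.
- **Noise does not favour a task.** This also stands. With equal means, a noisier MID makes the raw choice close to a coin toss. Systematic error needs higher gain, or a larger change with a disproportionately larger SD. No SD in the documents shows that either applies.
- **The size depends on the scenario.** When PFV has the larger change, as SA2 expects, disagreement is at most about 9% in the cases tried.
- **A significance requirement would filter most discordant calls.** If the paired difference had to reach p < 0.05, trials that both reach it and disagree would be about 1.2% of all trials in the 55% case and at most 0.4% in the equal-mean cases. The documents state neither that requirement nor selection by point estimate. Nor would it cure the gain-only case, where the difference is significant in about 40% of trials although the tasks are equally sensitive.

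A reader might also infer that the response is signed, so that equal and opposite changes would count as a difference in sensitivity. No passage says so: larger response can be read as magnitude, and no passage says that a paradigm-by-time contrast names the winner. Likewise, the documents contain no rule by which the trial would formally reject its own hypothesis.

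Finally, SA2 is a secondary outcome of a pilot, and later planners could compute t-scores if means and SDs are reported. That limits the harm, but Section 22.0 does not commit to reporting them.

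**Conclusion.** The mismatch holds. SA2 asks about sensitivity, the endpoint and its analysis use unstandardised change, and no section reconciles them. Following the stated endpoint can name a task that detects naltrexone no better, or worse.

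Confidence is high for the mismatch and low for its magnitude. The range from about 0.3% to 55% rests wholly on assumed means, SDs and correlation, and on selection by point estimate. The definition should be corrected before the data are analysed; it does not put the primary outcome at risk.

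**What to change.** **Section 4.0.** Define OPTIMAL PARADIGM as the paradigm with the larger absolute standardised within-person change, |mean change| / SD of change. With the same participants in both tasks, this ranks them as the paired t-score does. Evaluate it in one a priori reward ROI or ROI composite, applied to both tasks and fixed before any pre/post change is analysed. The choice needs a short justification, because the tasks are expected to engage different regions and a single region may suit one of them.

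**Section 22.0.** Report the PFV minus MID difference in this measure with a 95% CI from a bootstrap that resamples participants; a bootstrap is already planned for SA3. Report each task's mean change, its sign and its SD. Keep the %BOLD mixed model as a supporting analysis.

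**Cost.** Wording in two sections and one further bootstrap on data already collected. The interval will be wider and less familiar than a mixed-model contrast. The absolute standardised change is biased upward near zero, which a simple bootstrap does not remove and the report should say.
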